6.10.1.3. Serious Adverse Events

A serious adverse event (SAE) is defined as any untoward medical occurrence in an enrolled subject, regardless of its causal relationship to the IMP that results in death, is immediately life-threatening, requires in subject hospitalization or prolongation of existing hospitalization, results in persistent or significant disability or incapacity, or is a congenital anomaly or birth defect. Important medical events that may not meet these criteria may be considered SAEs when, based on appropriate medical judgment, they may jeopardize the subject or may require medical or surgical intervention to prevent one of the outcomes listed in this definition.

Numbers and percentages of subjects with SAEs will be presented. Summary of SAEs will be presented by SOC and PT. These tables are to include overall totals for AEs within each organ class.

The incidence of SAEs table will include only one occurrence of a preferred term (PT) per subject. If a subject report the same PT multiple times, then that the subject will be counted once under the PT. If a subject report multiple SAEs within the same SOC, then the subject will be counted once under that corresponding SOC.

ADVM-043 related SAEs will also be presented in a similar manner.

In Mock Shell: Table 14.3.2.2 and Table 14.3.2.3

6.10.1.4. Death

Any death during this trial will be collected and presented in a listing.

The information that is presented will include date of death, PT, and days on trial since the treatment administration on Study day 0.

In Mock Shell: Listing 16.2.7.5

6.10.2. Clinical Laboratory Evaluations

Clinical laboratory assessments will include hematology, chemistry, coagulation, and urinalysis. Analysis will be performed by the central laboratory. The laboratory evaluation schedule is shown on the Schedule of Assessments (Appendix 13.1).

A descriptive summary of the laboratory results along with change from baseline will be provided.

Shift in clinical laboratory evaluations will be summarized by low, normal and high.

6.10.2.1. Hematology

A descriptive summary of the hematology results along with the change from baseline will be presented. The following laboratory tests will be included in hematology analysis:

[REDACTED]

Shift in abnormality in hematology values will be summarized by minimum and maximum post-baseline abnormal category. Clinical laboratory evaluations will be summarized by low, normal and high.

A listing will present all hematology parameter values for all subjects.

In Mock Shell: Table 14.3.3.1, Table 14.3.3.6 and Listing 16.2.8.1

6.10.2.2. Serum Chemistry

A descriptive summary of the chemistry results along with the change from baseline will be presented. The following laboratory tests will be performed:

[REDACTED]

Liver Function Tests ALT and AST will be presented separately. Other chemistry parameters will be presented separately.

The shift table of liver function tests will be summarized by cohort group for the following categories based on the maximum value of AST and ALT of any post-baseline assessments relative to their baseline categories:

- 1 – 1.5x upper limit of normal (ULN)
- >1.5 – 2.0x upper limit of normal (ULN)
- >2.0 – 3x upper limit of normal (ULN)
- >3.0 – 5x upper limit of normal (ULN)
- >5x upper limit of normal (ULN)

Shift in abnormality in chemistry values other than ALT and AST will be summarized by minimum and maximum post-baseline abnormal category. Clinical laboratory evaluations will be summarized by low, normal and high.

A listing will present chemistry values for all subjects.

In Mock Shell: Table 14.3.3.2, Table 14.3.3.3, Table 14.3.3.7, Table 14.3.3.8 and Listing 16.2.8.2

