4.1.2 Exclusion Criteria

Subjects meeting any of the following criteria are to be excluded.

- 1) Forced expiratory volume in 1 second (FEV1) < 35 percent of predicted value at the Screening visit
- 2) Receiving systemic corticosteroids or other immunosuppressive medications
- 3) Immunodeficiency disease or evidence of active infection of any type, including human immunodeficiency virus
- 4) Evidence of major central nervous system, major psychiatric, musculoskeletal, or immune disorder
- 5) History of myocardial infarction within the past 1 year
- 6) History of cancer within the past 5 years, other than treated nonmelanomatous carcinoma of the skin and treated carcinoma in situ (CIS) of the cervix
- 7) Any clinically relevant abnormality evidenced by the screening hepatic ultrasound and/or chest x-ray
- 8) Within 24 hours of study treatment administration, evidence of active infection deemed clinically significant by the Investigator based on clinical exam and/or temperature > 38.5°C
- 9) Creatinine > 2 mg/dL.
- 10) Alanine transaminase (ALT) or aspartate transferase (AST) above the upper limit of normal at the Screening and the Baseline visits.
- 11) Total bilirubin > 1.5 × ULN, except for Gilbert's syndrome
- 12) Alkaline phosphatase > 2.5 × ULN
- 13) Diabetes with HbA1c >7%
- 14) Presence or history of hepatitis B or hepatitis C infection (HBsAg-positive or HCV-RNA positive)
- 15) Evidence of chronic liver disease

- 16) Organ or stem cell transplant recipient or awaiting transplantation
- 17) Participation in another current or previous gene transfer study
- 18) AAVrh.10 neutralizing antibody titer $\geq 1:5$
- 19) Other significant laboratory abnormalities or medical condition that the investigator feels may compromise the subject's safety
- 20) Female who is pregnant or lactating
- 21) History of alcohol or drug abuse within the past 5 years
- 22) Any history of allergies that may prohibit study-specific investigations; e.g., allergy to medications used for bronchoscopy
- 23) Receiving an investigational medicinal product (IMP) or participating in another investigational study with an IMP within 3 months prior to consent
- 24) Cigarette smoking, or any other tobacco use, or use of e-cigarettes or other recreational inhalant within 1 year of the Screening Visit.
- 25) Transfusion with human blood- or plasma-derived products within 8 weeks before scheduled Day 0 (treatment administration)

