13.2 Appendix: Assessment & Management of Potential Acute Liver Injury

In the event a subject develops $ALT > 2 \times ULN$, the study site will make every reasonable attempt to have the subject return to the clinic within 24 hours and conduct the following investigations:

Repeat liver function tests

Hepatitis A IgM

Hepatitis B surface antigen and hepatitis B core IgM

Hepatitis C RNA.

Cytomegalovirus IgM

Epstein-Barr viral capsid antigen IgM (if unavailable, obtain heterophile antibody or monospot testing)

Hepatitis E IgM

Serum creatine phosphokinase (CPK) and lactate dehydrogenase (LDH)

Measure direct bilirubin if total bilirubin $\geq 2 \times ULN$

Measure INR

Full blood count including differential white cell count for eosinophilia

Anti-nuclear antibody, anti-smooth muscle antibody, and Type 1 anti-liver kidney microsomal antibodies

Liver imaging (magnetic resonance) to evaluate liver disease

If acetaminophen is a potential contributor, measure serum acetaminophen adduct HPLC assay if available locally

Record the appearance or worsening of clinical symptoms of hepatitis (jaundice, fatigue, nausea, vomiting, right upper quadrant pain or tenderness, fever, rash or eosinophilia) on the Adverse Events eCRF.

Record use of concomitant medications, acetaminophen, herbal remedies, other-over-the-counter medications, or putative hepatotoxins on the Concomitant Medications eCRF.

Record alcohol use.

Monitor subjects at least weekly until liver chemistries (ALT, AST, alkaline phosphatase, total and direct bilirubin) resolve, stabilize, or return to within baseline values.

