4.2. Study Endpoints

4.2.1 Safety Endpoints

Type, frequency, severity, duration, and relationship to study drug of any AEs and laboratory abnormalities graded according to the National Cancer Institute Common Terminology Criteria for Adverse Events (CTCAE) version 4.03.

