5.4.9. Laboratory Abnormalities

The standard laboratory results will be compared against the standard low/high ranges reported.

If result < the low range, then, the result will be flagged as 'Low'. If the result is > the high range then, the result will be flagged as 'High'. Otherwise, the result is between the low and high ranges and will be flagged as 'Normal'.

Minimum and Maximum post-baseline abnormalities will also be flagged for each subject.

For urinalysis parameters, the results will be categorized as 'Normal' and 'Abnormal'.

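### The safety endpoint names CTCAE-graded laboratory abnormalities, but the readable SAP grades no laboratory value, and its low/normal/high shift tables cannot show severity

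*SAP*

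**What the plan says.** **Endpoint.** SAP 4.2.1, matching Protocol 2.2.1, defines the safety endpoint as the type, frequency, severity, duration and relationship of "any AEs and laboratory abnormalities graded according to the National Cancer Institute Common Terminology Criteria for Adverse Events (CTCAE) version 4.03". Safety after intravenous dosing is the primary objective.

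**Laboratory flags.** SAP 5.4.9 flags standard laboratory results against the reference range only: "If the result is > the high range then, the result will be flagged as 'High", with matching rules for Low and Normal. It uses no grade and no multiple of the upper limit of normal (ULN).

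**Shift tables.** The general rule in SAP 6.10.2 is "Shift in clinical laboratory evaluations will be summarized by low, normal and high". SAP 6.10.2.1 applies it to hematology. In SAP 6.10.2.2, ALT and AST get five ULN bands (1–1.5, >1.5–2, >2–3, >3–5 and >5 × ULN). For the rest: "Shift in abnormality in chemistry values other than ALT and AST will be summarized by minimum and maximum post-baseline abnormal category", again as low, normal and high.

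**Entry limits.** Protocol 4.1.2 excludes "Total bilirubin > 1.5 × ULN, except for Gilbert's syndrome" and "Alkaline phosphatase > 2.5 × ULN", so values above normal but within those limits are eligible.

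**Other outputs.** SAP 6.10.2.2 also plans descriptive summaries of values and of change from baseline, and "A listing will present chemistry values for all subjects". SAP 6.10.1.2 tabulates treatment-emergent AEs by CTCAE grade.

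**The concern.** The endpoint names a severity scale for laboratory abnormalities, and no readable SAP table applies that scale to laboratory values. The shift table sets each subject's worst result against baseline, but with three levels it shows only whether a limit was crossed. A subject who enters with a raised bilirubin or alkaline phosphatase has no higher category to move into.

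The product is a liver-directed vector, and liver injury is the harm the protocol plans for: section 3.10 suspends enrollment for it and section 13.2 sets out a work-up. That appendix follows both tests alongside the transaminases: "Monitor subjects at least weekly until liver chemistries (ALT, AST, alkaline phosphatase, total and direct bilirubin) resolve, stabilize, or return to within baseline values". At stake is whether the tabulated results show the severity of a laboratory change, or whether a reader must work it out from the listing.

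**Working it through.** No sample size, power or error rate bears on this point. The check applies the SAP's flag rule to baselines that the eligibility criteria allow, then compares the result with the SAP's own ALT/AST bands. The documents do not reproduce the CTCAE cut-points, so the ULN bands serve as the finer scale for illustration.

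**Inputs**
- High means above the upper reference limit (SAP 5.4.9).
- Bands: 1–1.5, >1.5–2, >2–3, >3–5 and >5 × ULN (SAP 6.10.2.2). A ≤1 × ULN row is added here because the listed bands lack one, giving six ordered categories.
- Eligible raised baselines (Protocol 4.1.2): bilirubin above 1 and up to 1.5 × ULN, with no limit in Gilbert's syndrome; alkaline phosphatase above 1 and up to 2.5 × ULN.
- Assumption: both tests belong to the redacted chemistry panel. The entry limits and Protocol 13.2 make this reasonable.

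**Step 1. Higher categories available = number of categories − position of the baseline category**

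| Baseline | Low/normal/high | Six ULN categories |
|---|---|---|
| Normal | 3 − 2 = 1 | 6 − 1 = 5 |
| Bilirubin >1 to 1.5 × ULN | 3 − 3 = 0 | 6 − 2 = 4 |
| Alkaline phosphatase >1 to 1.5 × ULN | 0 | 6 − 2 = 4 |
| Alkaline phosphatase >1.5 to 2 × ULN | 0 | 6 − 3 = 3 |
| Alkaline phosphatase >2 to 2.5 × ULN | 0 | 6 − 4 = 2 |

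**Step 2. Largest fold-rise that leaves the category unchanged**
- High under SAP 5.4.9: no upper bound.
- Closed ULN bands, upper limit ÷ lower limit: 1.5/1 = 1.5; 2/1.5 = 1.33; 3/2 = 1.5; 5/3 = 1.67. Only the band above 5 × ULN is unbounded.

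**Step 3. Illustrative subjects (the post-baseline values are assumed)**

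| Change (× ULN) | Planned table | Banded table |
|---|---|---|
| Bilirubin 1.2 to 4 | High to High | 1–1.5 to >3–5 |
| Alkaline phosphatase 2.5 to 6 | High to High | >2–3 to >5 |
| Bilirubin 1.0 to 1.6 | Normal to High | ≤1 to >1.5–2 |
| Bilirubin 1.0 to 12 | Normal to High | ≤1 to >5 |
| Alkaline phosphatase 2.5 to 2.6 | High to High | >2–3 to >2–3 |

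The third and fourth rows share one cell in the planned table. The last row shows that the bands also miss a small change.

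**Step 4. Number of subjects.** The planned maximum of 25 is reproduced as 4 cohorts × 5 plus 5 in Part B. The SAP states that Cohort 4 was not enrolled and Part B did not proceed. Three cohorts of 2 to 5 give 3 × 2 = 6 to 3 × 5 = 15 subjects, assuming no replacements. The documents do not say how many had a raised baseline.

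**The case against.** **The AE route may already deliver the endpoint.** Duration and relationship are AE attributes, which suggests that laboratory abnormalities were meant to be captured as AEs. Protocol 7.0 can be read as requiring any abnormal laboratory result to be recorded as an AE, with clinically significant worsening as one included case. Those AEs are CTCAE-graded and tabulated by cohort. This argument carries weight and lowers the importance of the point. It does not remove it. The section is ambiguous, the route depends on what the investigator reports, and findings associated with the underlying disease are exempt unless more severe than expected. The exclusions for chronic liver disease and for relevant ultrasound abnormalities limit how far that exemption reaches.

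**Other outputs show the size of a rise.** This is correct. The descriptive summaries include the minimum and maximum, and in a cohort of two the minimum and maximum change are the two subjects' own changes. The listing holds every value and can be read through at this sample size. None of these outputs is a laboratory-derived grade.

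**Banding only ALT and AST is principled.** The readable numerical thresholds that trigger liver management or suspension are ALT-based (1.5, 2 and 5 × ULN), and the bands contain them. Bilirubin at 2 × ULN or more only prompts a direct bilirubin test within the ALT work-up. This explains the choice of bands but does not supply the severity scale that the endpoint names.

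**Stronger readings.** A reader might infer that liver signals would be lost, that unscheduled results are left out, or that dose escalation was compromised. The documents support none of these. The values are summarized and listed. SAP 5.4.2 includes all available safety data. The protocol synopsis has the DMC review by-subject data before each escalation, so its review does not depend on these shift tables.

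**Conclusion.** The point holds as a minor reporting weakness. The endpoint and the planned laboratory tables do not match: no readable SAP section turns a laboratory value into a CTCAE grade. Low/normal/high shift tables for hematology and for chemistry other than ALT and AST cannot show severity. For an eligible raised bilirubin or alkaline phosphatase, every further rise reads High-to-High.

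The effect is confined to how results are tabulated. No value, estimate or decision rule changes, and the number of subjects affected cannot be determined from the documents.

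The High-to-High result for these two tests assumes that both are in the redacted panel. The wider mismatch does not need that assumption, but it does assume that the redacted text and the unavailable mock shells contain no laboratory grading.

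**What to change.** In SAP 5.4.9 and 6.10.2, derive CTCAE v4.03 grades for the gradable laboratory analytes, hematology included, and at minimum for total bilirubin and alkaline phosphatase. Tabulate baseline grade against worst post-baseline grade by cohort. State that the worst value is taken over any post-baseline assessment, including unscheduled tests.

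If the ALT/AST bands are used for these two tests instead, add a ≤1 × ULN row. ALT and AST must be normal before dosing (Protocol 6.4.2), so that is the row where a compliant ALT/AST baseline sits. Bands would show the degree of change, but they are not CTCAE grades and so meet the endpoint less fully.

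An optional addition is a by-subject display of baseline and peak ALT and total bilirubin in multiples of ULN, with study day and a note of Gilbert's syndrome. It would have at most about 15 rows.

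The cost is SAP wording and minor programming from data already collected, with no new procedure for subjects.

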6.10.2.3. Urinalysis

A descriptive summary of the hematology results along with the change from baseline will be presented. Continuous and categorical summaries will be presented separately.

The following laboratory will be included for urinalysis:

pH, specific gravity and urobilinogen values will be summarized.

Shift in abnormality in urinalysis values will be summarized by minimum and maximum post-baseline abnormal category. Clinical laboratory evaluations will be summarized by normal and abnormal.

The urinalysis parameter values will be listed for all subjects in FAS population.

In Mock Shell: Table 14.3.3.4.a, Table 14.3.3.4.b, Table 14.3.3.9 and Listing 16.2.8.3

6.10.2.4. Coagulation

A descriptive summary of the coagulation results along with the change from baseline will be presented.

A listing will be provided for coagulation tests by subject and visit.

In Mock Shell: Table 14.3.3.5 and Listing 16.2.8.4

6.10.2.5. Other Laboratory Assessments

[REDACTED]

[REDACTED]

Pregnancy test results will be listed by subject.

In Mock Shell: Table 14.3.4.4 and Listing 16.2.8.5

6.10.3. Electrocardiogram

A 12-lead ECG measurement will be obtained using an automatic machine while the subject is in the supine position, after the subject has been resting supine for at least 5 minutes. Electrocardiograms are to be evaluated for clinically significant abnormalities (as defined in [section 5.4.10](#)), including [REDACTED].

Abnormality in ECG parameters collected will be summarized for the following parameters: Ventricular Rate (Beats/Min), P-R Interval (msec), QRS Duration (msec), Q-T Interval (msec), Q-Tc Interval (msec) and overall interpretation.

All ECG results will be listed by dose cohort and subject.

In Mock Shell: Table 14.3.4.1 and Listing 16.2.8.8

6.10.4. Vital Sign Measurements

Vital signs will include body weight, BMI, systolic and diastolic blood pressure, heart rate, respiratory rate and oral body temperature.

Clinically significant abnormalities in vital sign measures across all post-baseline assessments as defined in [section 5.4.11](#) are to be summarized for all the parameters.

A descriptive summary of all the vital sign parameters along with change from baseline will be presented by dose cohort.

All vital sign results will be listed by dose cohort and subject. Abnormal results will be highlighted.

In Mock Shell: Table 14.3.4.2, Table 14.3.4.3 and Listing 16.2.8.6

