5.4.10. PCS Abnormalities Criteria: ECG

The criteria for potentially clinically significant (PCS) abnormalities are shown in the following table:

ECG: Criteria for PCS Abnormalities
Ventricular Rate (Beats/Min) 
• <45• >100
P-R Interval (msec) 
• <100• >200
QRS Duration (msec) 
• < 80• > 200
Q-T Interval (msec) 
• <250• >500
Q-Tc Interval (msec) 
• <250• >500

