5.4.11. PCS Abnormalities Criteria: Vital Signs

The criteria for clinically relevant vital signs abnormalities are shown in the following table:

Vital Signs: Criteria for PCS Abnormalities
Systolic Blood Pressure 
• <90 mmHg• >180 mmHg
Diastolic Blood Pressure 
• <50 mmHg• >100 mmHg
Temperature 
• <36 ° C• >38 ° C
Heart Rate 
• <40 beats per minute• > 100 beats per minute
Respiratory Rate 
• <12 breaths per minute• >20 breaths per minute

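### The vital-sign abnormality summary takes no account of pre-dose status, so a long-standing abnormality is tabulated like a new one

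*SAP*

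**What the plan says.** For vital signs, SAP 6.10.4 plans three displays:

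- A summary of "Clinically significant abnormalities in vital sign measures across all post-baseline assessments". SAP 5.4.11 supplies the limits: "The criteria for clinically relevant vital signs abnormalities are shown in the following table". All of them are absolute, for example respiratory rate below 12 or above 20, heart rate below 40 or above 100, and temperature below 36 or above 38 °C.
- Descriptive statistics for every parameter within each cohort, both as measured and as the difference from the baseline value.
- A listing: "All vital sign results will be listed by dose cohort and subject. Abnormal results will be highlighted".

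For ECG, SAP 6.10.3 states: "Abnormality in ECG parameters collected will be summarized for the following parameters". SAP 5.4.10 again gives absolute limits. Section 6.10.3 names no visits and plans neither a shift nor a change from baseline.

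The laboratory sections differ. ALT and AST are tabulated "based on the maximum value of AST and ALT of any post-baseline assessments relative to their baseline categories" (SAP 6.10.2.2), and for hematology "Shift in abnormality in hematology values will be summarized by minimum and maximum post-baseline abnormal category" (SAP 6.10.2.1). Other chemistry and urinalysis also have shift summaries.

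**The concern.** With no control group, each subject's own pre-dose state is the only reference for judging whether an abnormal reading followed treatment. The vital-sign abnormality summary does not use that reference. A reader of the table alone cannot tell a subject whose respiratory rate was above 20 before dosing and stayed there from one whose rate rose above 20 after ADVM-043.

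Eligibility does not rule out the first kind of subject. Protocol 4.1 sets no limits on blood pressure, heart rate or respiratory rate, and it admits subjects with FEV1 as low as 35% of predicted. The one numeric temperature exclusion is above 38.5 °C, whereas the SAP flags anything above 38 °C. The investigator may still exclude a subject on general safety grounds, so this shows only that such subjects are possible, not that they are common.

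At stake is how a safety table is read in very small cohorts, where one subject moves the percentage a long way.

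**Working it through.** The plan gives no figure to reproduce: SAP 5.1 states that no formal sample size calculation was made. The check is a comparison of rules, followed by simple proportions.

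**1. Is pre-dose status part of the rule?**

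| Data | Where | Pre-dose status used? |
|---|---|---|
| ALT, AST | SAP 6.10.2.2 | Yes: worst post-baseline category against baseline category |
| Hematology, other chemistry, urinalysis | SAP 6.10.2.1 to 6.10.2.3 | Yes: shift in abnormality |
| Treatment-emergent AEs | SAP 5.4.7 and 6.10.1 | Yes: by definition a pre-existing event must worsen |
| Vital-sign abnormalities | SAP 6.10.4 with 5.4.11 | No: post-baseline readings against absolute limits |
| ECG abnormalities | SAP 6.10.3 with 5.4.10 | Not stated, and visits not stated |

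**2. What the vital-sign rule does.** Take two subjects. Subject A has a respiratory rate above 20 before dosing and the same rate afterwards. Subject B is between 12 and 20 before dosing and above 20 afterwards. Under SAP 6.10.4 both are post-baseline abnormalities. In a shift table A falls in the high-to-high cell and B in the normal-to-high cell.

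**3. Weight of one subject.** SAP 5.1 plans 2 to 5 subjects per cohort. SAP section 6 excludes Part B and Cohort 4, which leaves Cohorts 1 to 3, or at most 3 × 5 = 15 subjects at 5 per cohort. One subject like A therefore contributes:

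- 2-subject cohort: 1/2 = 50%
- 5-subject cohort: 1/5 = 20%
- total column at 15: 1/15 = 6.7%

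**4. Which reading is baseline?** Protocol 6.4.2 takes vital signs at the Baseline Visit, and Protocol 6.4.3.1 takes them again on Day 0 before treatment. SAP 5.4.1 defines the Baseline visit but does not say which of the two readings is the baseline value. A pre-dose Day 0 reading could therefore be handled as post-baseline.

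**5. ECG.** Protocol 13.1 schedules ECGs at Screening and Week 52 only. If all collected ECGs were pooled, pre- and post-treatment results would be mixed. If they were shown by visit, they would not be. Section 6.10.3 does not say which.

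**The case against.** The strongest reply is that baseline is already covered elsewhere. SAP 6.10.4 itself plans change from baseline and a listing with abnormal values highlighted, and with at most 15 subjects at 5 per cohort a reader can trace each case by hand. Protocol 7.0 also sends clinically significant worsening into AE reporting. All of this stands, and it keeps the point small. It does not repair the table: a mean change does not show who newly crossed a limit, and a count that must be corrected from a listing is not doing its job.

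A second reply is that the exact counting rule is inferred. Section 6.10.4 does not say whether subjects or readings are counted, and the mock shells (Tables 14.3.4.2 and 14.3.4.3) are not in the documents; they may carry a baseline row. That is fair. However, the SAP text contains no baseline condition under either counting unit, and if the shells do contain one, the text should say so.

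Three stronger readings are tempting and are not supported:

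- *That ECG abnormalities present before dosing will be reported as post-treatment findings.* Section 6.10.3 does not restrict the summary to post-baseline ECGs. A by-visit table would place Screening beside Week 52, which is what is wanted. Only the unstated visit scope can be criticized.
- *That the frequency of the problem can be computed from the number of visits.* Assuming a chance q of crossing a limit independently at each visit describes intermittent crossings, not a persistent pre-dose abnormality. Under that model a fraction 1 − q of the counted subjects would have a normal baseline reading and would still count as new after the fix. No value of q stands in the documents.
- *That the primary safety conclusion or a dosing decision is compromised.* The safety endpoint (SAP 4.2.1) is AEs and graded laboratory abnormalities. The dose-limiting toxicity and suspension rules (SAP 4.3) use AEs and ALT.

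**Conclusion.** The point holds for vital signs. The abnormality summary in SAP 6.10.4 cannot separate pre-existing from new abnormalities, and in this respect it departs from the SAP's own laboratory shift tables and treatment-emergent definition. One pre-existing case that does not worsen is 50% of a 2-subject cohort or 20% of a 5-subject cohort. The number of such cases is unknown and cannot be estimated from the documents.

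This conclusion rests on the SAP text as written, without the mock shells. Its consequence is limited to descriptive interpretation: no formal testing is planned and no decision rule uses the table. It is a cheap improvement rather than a serious flaw. For ECG, all that holds is that the visit scope and the handling of the Screening result are unstated.

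**What to change.** - **SAP 6.10.4:** tabulate baseline category by worst post-baseline category (low, within limits, high) for each vital sign that has limits in SAP 5.4.11. Alternatively, count new or worsened abnormalities and show the baseline count beside them, with a stated rule for what counts as worsened.
- **Baseline value:** define it as the last reading before dosing, so that the pre-dose Day 0 reading cannot be classed as post-baseline.
- **SAP 6.10.3:** state which visits are summarized, and present Screening and Week 52 separately.

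No new data are needed. The cost is a layout change in two tables and one definition. The drawback is that cohorts of 2 to 5 subjects will leave many shift cells empty; the alternative of paired counts is more compact. Neither layout removes crossings that occur intermittently in a subject whose baseline reading happened to be normal, so the by-subject listing should stay.
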